In preliminary work, we have shown that we can quantitatively measure myocardial blood flow reserve, oxidative metabolism and myocardial fibrosis through non-invasive cardiac imaging. Myocardial blood flow reserve can be quantitatively measured with cardiac magnetic resonance imaging (cMRI) and positron emission tomography (PET). The mono-exponential

decay rate (K_{mono}) of ^{11}C -Acetate determined with PET is a validated measure of myocardial oxidative metabolism. Fibrotic myocardium can be quantified using cMRI T1 mapping.

We postulate that reduced myocardial blood flow reserve contributes to impaired oxidative metabolism and increased myocardial fibrosis in HFpEF. We propose to test the following primary hypotheses: 1) Compared to healthy and hypertensive individuals, subjects with HFpEF have reduced myocardial blood flow reserve, 2) Compared to healthy and hypertensive individuals, subjects with HFpEF have reduced oxidative metabolism; 3) Compared to healthy and hypertensive individuals, subjects with HFpEF have increased myocardial fibrosis, and 4) Myocardial blood flow reserve is positively correlated with oxidative metabolism and inversely correlated with myocardial fibrosis.

Aim 1. To compare myocardial blood flow reserve in individuals with HFpEF versus those with hypertension and healthy individuals. We will enroll 60 subjects (20 HFpEF, 20 hypertensive, and 20 healthy) who will undergo cMRI and ^{13}N -Ammonia PET to quantify myocardial blood flow at rest and during pharmacologic stress with regadenoson.

Aim 2. To compare myocardial oxidative metabolism in individuals with HFpEF versus those with hypertension and healthy individuals. Subjects enrolled in aim 1 will also undergo ^{11}C -Acetate PET imaging to quantify oxidative metabolism via the mono-exponential decay rate of ^{11}C -Acetate.

Aim 3. To compare myocardial fibrosis in individuals with HFpEF versus those with hypertension and healthy individuals. Subjects enrolled in aim 1 will also undergo cMRI with T1 mapping to quantify myocardial fibrosis.

Aim 4. To assess the relation between myocardial blood flow reserve, oxidative metabolism and fibrosis. The correlations between myocardial blood flow reserve, oxidative metabolism and fibrosis will be evaluated.

2. Study Design

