13N-Ammonia Positron Emission Tomography for the assessment of myocardial blood flow. 13N-Ammonia studies will be performed at rest and stress on a whole body PET/CT scanner as previously described.³⁸ An initial transmission scan will be obtained for the purpose of attenuation correction. Next, rest imaging will be initiated in list mode upon injection of 25mCi of intravenous 13N-Ammonia with serial images acquired over approximately 15-20 minutes. Approximately 50 minutes after the initial 13N-Ammonia injection (5 half-lives), imaging will be repeated following pharmacologic vasodilation with regadenoson (Astellas Pharma, Northbrook, IL). As with the cMRI protocol, 400 µg of regadenoson will be injected intravenously over 5-10 seconds, followed by a 5-10 ml saline flush. Approximately 60 seconds after the regadenoson injection, 25mCi of 13N-Ammonia will be injected with PET imaging in list mode. Heart rate, rhythm, and blood pressure will be monitored throughout the imaging protocol. Myocardial blood flow and coronary flow reserve will be quantified off-line using FlowQuant software (Ottawa Heart Institute, Ottawa, Canada).

Procedure/Activity	Frequency
Informed Consent	Once (at time of screening in clinic)
Blood draw	Once (at beginning of study visit – day 1)
Peripheral IV placement	Twice (at study visit on days 1 & 2)
Transthoracic Echocardiogram with contrast	Once (at study visit – day 1)
¹¹C-Acetate PET	Once (at study visit – day 1)
Cardiac MRI (rest, stress)	Once (at study visit – day 1)
Cardiac MRI (fibrosis imaging)	Once (at study visit – day 2)
¹³N-Ammonia PET (rest, stress)	Once (at study visit – day 2)

Reporting of clinical findings. As the imaging studies are being performed for research purposes, clinical reports will not be generated. However, if unexpected or previously unknown abnormalities of clinical importance are identified or urgent/emergent conditions are found, these will be clinically reported to both the patient and the patient’s physicians.

3. Statistical Methods

Aim 1. To compare myocardial blood flow reserve in individuals with HFpEF versus those with hypertension and healthy individuals.

Primary Hypothesis: Compared to healthy and hypertensive individuals, subjects with HFpEF have reduced myocardial blood flow reserve.

Secondary Hypotheses:

- A) Myocardial blood flow is progressively impaired from healthy, to hypertensive, to HFpEF.

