- B) Myocardial blood flow reserve by Gd enhanced cMRI (MPRI) is correlated with CFR by ¹³N-Ammonia PET.
- C) Subendocardial MPRI is lower than subepicardial MPRI in HFpEF.
- D) Subendocardial MPRI is progressively impaired from healthy to hypertensive to HFpEF.
- E) Myocardial blood flow reserve is positively correlated with LV diastolic function.
- F) Myocardial blood flow reserve is positively correlated with LV systolic function.

Analysis for aim 1. Primary outcome: Myocardial blood flow reserve, as measured by MPRI from contrast enhanced cMRI first pass perfusion imaging and CFR from ¹³N-Ammonia PET perfusion imaging will be compared between the three study groups: healthy, hypertensives, and HFpEF. The distributions of each within each study group will be assessed using histograms, Q norm plots, and the Shapiro Wilk test. If normally distributed then analysis of variance will be used to test for differences in myocardial blood flow reserve between groups. If the p-value from the ANOVA is < 0.05, then pairwise comparisons using unpaired t-tests with unequal variances will be made between groups using a Bonferroni correction. If MPRI or CFR is not normally distributed, then a Kruskal-Wallis test and Wilcoxon rank sum tests will be used in place of ANOVA and t-tests. The null hypothesis is that myocardial blood flow reserve does not differ among HFpEF patients, healthy individuals, and hypertensive individuals. We will also assess correlations (Spearman) between myocardial blood flow reserve, age, gender, blood pressure, heart rate, and body mass index. To account for potential confounders, multivariable linear regression models will be constructed with myocardial blood flow reserve as the dependent variable, study group as the primary independent variable, with adjustments for age, gender, race/ethnicity, anti-hypertensive medications, systolic blood pressure, heart rate, body mass index, LVEF, LV end diastolic volume, and LV mass. Prior to entry into models, variables will be log transformed, as appropriate. We will check model fit by residual plots. Missing data will not be imputed as we will attempt to replace subjects with significant amounts of missing data due to uninterpretable images, as detailed above.

Statistical power for Aim 1: Using a one-way ANOVA at $p = 0.05$, we present between group differences in myocardial blood flow reserve as assessed by CFR under different sample size and power scenarios in **Table 4**. We anticipate

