Healthy	Sample size		Power			SD
	HTN	HFpEF	0.90	0.80	0.70	
20	20	20	1.00	0.87	0.75	0.90
15	15	15	1.20	1.05	0.92	0.90
25	25	25	0.80	0.75	0.60	0.90

ANOVA calculations based upon mean estimated CFR in normals of 3.17 ± 0.88 .³⁹

having 80% power to detect a between group difference (largest to smallest) in mean values of CFR of 0.87, using a conservative estimate for the standard deviation of 0.90 when compared to those reported for normal controls and patients with hypertension, 0.68 and 0.88, respectively.³⁹ The between group difference in CFR is within the range of difference detected between normals (3.17 ± 0.68) and patients with hypertension (2.18 ± 0.88), previously reported.³⁹ Of note even if sample size is reduced by 25%, we still anticipate having good power to detect a between group difference of 1.05. Therefore, using conservative sample sizes that account for potential dropout or uninterpretable images, as well as larger estimates for standard deviation than previously reported, we should have good power to detect plausible differences in myocardial blood flow reserve between HFpEF, healthy, and hypertensive subjects.

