groups difference (largest to smallest) in T1 relaxation times of 60 msec, using a conservative estimate for the standard deviation of 60 msec, which was based on a 51 msec SD observed in a HFpEF population (mean T1 time 381msec).⁴¹ The difference in T1 relaxation times is well within the range of expected difference based upon reported values for normals (459 ± 38) in the MESA study and patients with HFpEF (381 ± 51).^{32, 41} Of note, even if sample size is reduced by 25%, we still anticipate having good power to detect a between group difference of 70 msec, which is still less than the clinical relevant difference of ~ 80 msec. Therefore, using conservative sample sizes, accounting for potential dropout or uninterpretable images, as well as a larger standard deviation estimate than previously reported, we should have good to excellent power to detect plausible differences in myocardial fibrosis between HFpEF, healthy, and hypertensive subjects.

Secondary analyses: The secondary hypotheses are detailed above and evaluate for progressive increases in myocardial fibrosis across study groups as well as the relationships between myocardial fibrosis and cardiac function. The analyses for myocardial fibrosis will follow the same statistical methods to those described for oxidative metabolism. Myocardial fibrosis, as assessed by T1 relaxation times, will be the independent variable and assessed in relation to features of diastolic and systolic function as previously defined above.

Aim 4. To evaluate the relationships between myocardial blood flow reserve, oxidative metabolism and fibrosis.

Primary Hypothesis: Myocardial blood flow reserve is positively correlated with oxidative metabolism and inversely correlated with myocardial fibrosis.

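### Table 4 (Aim 1 power for CFR) cannot be reproduced: the 25-per-group row fits no pattern of means, and 80% power for 0.87 depends on an unstated middle mean

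*Combined protocol and SAP*

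**What the plan says.** All of this is in Section 3, Statistical Methods, under the power paragraph for Aim 1 and Table 4.

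- **Test:** "Using a one-way ANOVA at $p = 0.05$, we present between group differences in myocardial blood flow reserve as assessed by CFR".
- **SD:** "using a conservative estimate for the standard deviation of 0.90", applied to every row of the table.
- **Headline claim at the planned 20 per group:** "having 80% power to detect a between group difference (largest to smallest) in mean values of CFR of 0.87".
- **Claim at 15 per group:** "even if sample size is reduced by 25%, we still anticipate having good power to detect a between group difference of 1.05". Table 4 lists 1.05 in the 80% column.
- **Table 4, differences for 90% / 80% / 70% power:** 1.00 / 0.87 / 0.75 at 20 per group, 1.20 / 1.05 / 0.92 at 15, and 0.80 / 0.75 / 0.60 at 25.
- **Footnote:** "ANOVA calculations based upon mean estimated CFR in normals of 3.17 ± 0.88". The text beside the table gives normals as 3.17 ± 0.68 and hypertensives as 2.18 ± 0.88.

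On the order of the groups, secondary hypothesis A says only "Myocardial blood flow is progressively impaired from healthy, to hypertensive, to HFpEF". No section gives an assumed HFpEF mean CFR or places the middle mean. Aim 3 words its power claim the same way, with 80% power for a "difference (largest to smallest) in T1 relaxation times of 60 msec" at an SD of 60 msec (Table 6).

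**The concern.** The power of a three-group ANOVA depends on all three means, not only on the gap between the largest and smallest. For a given gap, power is lowest when the middle mean is midway and highest when it coincides with an extreme. A table of detectable largest-to-smallest differences therefore needs that position stated. Table 4 does not state it, and its rows do not appear to share one.

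This is the only power statement for the Aim 1 primary outcome. If it cannot be rebuilt from one stated basis, a reader cannot tell whether the planned 20 per group has the claimed 80%, somewhat less, or more.

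**Working it through.** **Inputs (Section 3, Aim 1).** Three equal groups of n, alpha 0.05, SD σ = 0.90, and the stated largest-to-smallest difference d. The middle mean is not given. I write the means as 0, p·d and d, and let p run from 0.5 (midway) to 0 (equal to an extreme).

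**Formula.** The F statistic has 2 and 3n − 3 degrees of freedom and noncentrality λ = n·Σ(mᵢ − m̄)²/σ². This is n·d²/(2σ²) when the middle mean is midway and 2n·d²/(3σ²) when it is at an extreme. Power is the probability that the noncentral F exceeds the 5% critical value.

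**Step 1. The headline cell.** For n = 20 and d = 0.87, d² = 0.7569 and σ² = 0.81.

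- Midway: λ = 20 × 0.7569 / 1.62 = 9.34, power 76.4%.
- At an extreme: λ = 40 × 0.7569 / 2.43 = 12.46, power 87.8%.
- 80% needs λ = 10.16, which corresponds to p = 0.244.

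Simulation with 40,000 trials per scenario gave 76.8% and 87.7%. So 80% is attainable, but only for a position the plan does not state.

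**Step 2. All cells at SD 0.90.**

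| n per group | Stated d (90/80/70%) | Power, midway | Power, at an extreme |
|---|---|---|---|
| 20 | 1.00 / 0.87 / 0.75 | 87.5 / 76.4 / 62.7% | 95.2 / 87.8 / 76.0% |
| 15 | 1.20 / 1.05 / 0.92 | 89.4 / 79.4 / 67.5% | 96.2 / 90.0 / 80.4% |
| 25 | 0.80 / 0.75 / 0.60 | 79.3 / 73.6 / 53.1% | 89.9 / 85.6 / 66.2% |

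In the last row, 0.60 cannot reach 70% under any pattern. The 0.80 entry needs the middle mean at an extreme, while 0.75 needs it about 16% of the range in.

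**Step 3. A check that needs neither the SD nor the middle mean.** At fixed n, λ = c·n·d², where c absorbs both unknowns. The ratio of two detectable differences is then the square root of the ratio of the required λ values. For n = 25 the required λ is 13.20, 10.05 and 8.03 for 90%, 80% and 70%.

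- 90% to 80%: √(13.20/10.05) = 1.146. The row has 0.80/0.75 = 1.067.
- 80% to 70%: √(10.05/8.03) = 1.119. The row has 0.75/0.60 = 1.250.

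Rounding to the nearest 0.05 does not explain it. The first ratio could then be at most 0.825/0.725 = 1.138, and the second at least 0.725/0.625 = 1.160. Over all values of c, the best fit still leaves one cell of this row 4.8 points from target. For all nine cells of Table 4 together the figure is 7.5 points.

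**Step 4. The two differences in the 80% column that the text relies on.** Choose c so that d = 1.05 has exactly 80% power at n = 15. Then n = 20 needs d = 0.90, and 0.87 has 77.0%, whatever the SD or middle mean. Starting instead from 0.87 at n = 20, the entry at n = 15 should be 1.01.

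**Step 5. Which convention the plan seems to use elsewhere.** With the middle mean midway, the Table 6 entries (SD 60 msec) give 90.6 / 79.3 / 69.9% at 20 per group, 89.4 / 79.4 / 71.4% at 15 and 88.3 / 80.3 / 69.8% at 25. All nine are within 2 points of 90/80/70%. Table 6 claims 80% at 60/60 = 1.00 SD for 20 per group; Table 4 claims it at 0.87/0.90 = 0.97 SD. At 25 per group Table 6 stands at 1.00 / 0.90 / 0.80 SD, against 0.89 / 0.83 / 0.67 SD in Table 4.

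**Step 6. What the planned size can detect.** The plan cites 3.17 − 2.18 = 0.99 as the reported difference between normals and hypertensives. At n = 20 and SD 0.90 this has 86.8% power with the middle mean midway, and more otherwise.

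**The case against.** The strongest reply is that the headline figure is under-specified rather than wrong, since 80% for 0.87 lies inside the attainable range. With the middle mean about 24% from one extreme, the 20-per-group row gives 90.2 / 80.0 / 66.6% and the 15-per-group row 91.8 / 82.8 / 71.3%, so six of the nine cells come within 3.4 points of target. The text calls 1.05 good power and does not itself attach 80% to it. Midway is an inference from Table 6, which concerns a different endpoint. The 25-per-group row is not the planned size, and no sentence relies on it. The footnote SD does not enter the calculation, which uses 0.90.

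Much of this stands. Taken alone, the 0.87 claim is a gap in specification, the footnote is clerical, and the figure of 0.91 proposed below is conditional on midway. But the 24% position is stated nowhere, it differs from the basis that reproduces Table 6, and it leaves the 25-per-group row at 82.7 / 77.3 / 56.8%. The table does put 1.05 under 80%, so the mismatch of about 3 points with 0.87 remains.

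**Conclusion.** The concern holds. The 25-per-group row of Table 4 is an arithmetic error under every SD and every pattern of means. The claim of 80% power for 0.87 at the planned size is not determined by the stated inputs: it is 76.4% at minimum and 87.8% at maximum. If the midway convention that fits Table 6 is intended, the claim is 3.6 points too high and the 80% difference is 0.91. The footnote SD contradicts the text.

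These results assume normal data with a common SD of 0.90 and the omnibus F test at 0.05, as the plan states. The consequence is modest: 0.91 is still below the cited 0.99, and the adequacy of 20 per group is not in question. The power statement for a primary outcome should nevertheless be corrected.

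**What to change.** State where the middle group mean is assumed to lie and recompute every cell of Table 4 on that basis. If midway is meant, as Table 6 implies, the entries for 90% / 80% / 70% power at SD 0.90 are:

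| n per group | 90% | 80% | 70% |
|---|---|---|---|
| 20 | 1.04 | 0.91 | 0.81 |
| 15 | 1.21 | 1.06 | 0.95 |
| 25 | 0.92 | 0.81 | 0.72 |

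The text would then claim 80% power for a CFR difference of 0.91, or at least 76% for 0.87, and the 15-per-group sentence would read 1.06. If another position is intended, state it and give the matching figures. Correct the footnote so that the normal mean of 3.17 carries an SD of 0.68.

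The cost is restating figures only. Sample size, allocation and analysis stay as they are.

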
Arrive at CRC (fasting > 6 hours)
 
History and Physical
 
Venous blood draw/Peripheral IV
 
Transthoracic Echocardiogram
 
¹¹C-Acetate PET
 
Cardiac MRI (rest, stress)
	
Arrive at Cardiac MRI suite
 
Peripheral IV
 
Cardiac MRI (fibrosis imaging)
 
¹³N-Ammonia PET (rest, stress)

Echocardiography: At the start of echocardiography, heart rate and blood pressure will be recorded. A registered cardiac sonographer will perform comprehensive 2D, M-mode, and Doppler transthoracic echocardiography following a pre-specified protocol. A minimum of 3 complete cardiac cycles will be recorded for each image. Images will be acquired using a Phillips IE33 (Phillips Corp, Andover, MD) machine and data will be stored digitally for off-line analysis using commercially available software (HeartLab, AGFA and Cardiac Performance Analysis, TomTec). Quantification of cardiac structure and function will be performed in accordance with guidelines from the American Society of Echocardiography.¹¹⁻¹³ In particular, LV size and wall thicknesses will be measured using the 2D method, while LV volumes will be measured from the apical 4 and 2 chamber views via the Simpson’s Biplane method. LV ejection fraction will be calculated as LV stroke volume/end diastolic volume. To optimize assessment of left ventricular volumes and ejection fraction, intravenous echocardiographic contrast (Definity, Lantheus Medical Imaging, N Billerica, MA) will be given. LV mass will be calculated using the Devereux formula as recommended by the American Society of Echocardiography.¹⁴ Diastolic function will be assessed using mitral annular tissue Doppler e’ velocities, transmitral spectral Doppler E wave velocity and deceleration time, and the ratio of E and A wave velocities, as well as isovolumic relaxation time, and left atrial pressures (defined as E/e’). LV systolic function will be assessed by LVEF, mitral annular tissue Doppler S’ velocities, and speckle tracking derived global longitudinal strain and strain rates, which are less angle and load dependent when compared to LVEF and tissue Doppler analyses. Our group has previous experience in quantitative echocardiography, including speckle tracking.¹⁵⁻¹⁸

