Cardiac Magnetic Resonance Imaging of myocardial blood flow and myocardial fibrosis. cMRI will be performed on a 1.5T Siemens Magnetom Avanto scanner (Siemens, Erlangen, Germany). Subjects will be scanned with a phased array torso receiver coil. Following localizer images for identification of the heart within the thorax, cine imaging (“steady state free precession”) will be performed to generate conventional 4 and 2 chamber views, as well as short axis images. A short axis “stack” of cine images from the base to apex of the heart will be obtained, from which LV wall thickness, mass, volumes, and ejection fraction will be determined. Typical acquisition parameters will be used: field of view 300x340mm, matrix 156x192, slice thickness 8 mm, flip angle 80° with downward adjustment depending upon the specific absorption rate, echo time 1.1ms, bandwidth 930Hz/pixel, and at least 30 phases per cycle to maintain a repetition time < 50 ms. Parallel imaging will be used with generalized autocalibrating partially parallel acquisition (GRAPPA) using an acceleration factor of 2.6

Following cine imaging, myocardial perfusion imaging will be performed at rest following dual bolus (pre bolus =0.005 mmol/kg; main bolus = 0.05 mmol/kg) intravenous injection of Gadobutrol (Gd-DO3A-butrol: Gadavist, Bayer Healthcare Pharmaceuticals, Wayne, IN), as previously described.²³⁻²⁷ First pass imaging of the wash in of Gd-DO3A-butrol through the LV myocardium will be obtained in 3 short axis imaging planes centered at the mid LV at the level of the papillary muscles, the basal LV below the mitral valve, and apical LV. T1 weighted saturation-recovery turbo fast low angle shot (FLASH) gradient echo sequences will be used for myocardial perfusion imaging. All short axis images for myocardial perfusion imaging will be

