Secondary analyses: The secondary hypotheses are presented above. In addition to testing the primary hypothesis for between group differences in myocardial blood flow reserve, we will also evaluate for a significant trend across the three study groups using Spearman correlation. The relationships between myocardial blood flow reserve derived from cMRI (MPRI) and PET (CFR) will be compared by Spearman correlation as well as intraclass correlation in all subjects and by subject group. Using ANOVA, we will also assess whether subendocardial MPRI is lower in HFpEF as compared to healthy and hypertensive controls. Similarly we will assess whether subendocardial MPRI is lower than subepicardial MPRI among HFpEF subjects using paired t-tests. The relationships between myocardial blood flow reserve and cardiac function will also be evaluated. Scatterplots and Spearman correlations will be performed with myocardial blood flow reserve as the independent variable and measures of diastolic function as the dependent variables (mitral annular tissue Doppler e' velocities, isovolumic relaxation time, transmitral spectral Doppler E wave velocity, and E/e'). A nominal p-value threshold of < 0.05 will be used for all correlations and results meeting significance at the nominal threshold will be considered for follow up study. Similarly, we all also examine scatterplots and Spearman correlations between myocardial blood flow reserve and systolic function (LVEF, mitral annular tissue Doppler s' velocities, and global longitudinal strain). For both systolic and diastolic parameters, we will perform multivariable linear regression analyses adjusting for age, gender, race/ethnicity, systolic blood pressure, heart rate, body mass index, LVEF, LV end diastolic volume, and LV mass. We will also test for effect modification on the relationships between myocardial blood flow reserve and diastolic and systolic function by including multiplicative interaction terms in the linear regression models. Prior to entry into regression models non-normally distributed variables will be appropriately transformed.

Aim 2. To compare myocardial oxidative metabolism in individuals with HFpEF versus those with hypertension and healthy individuals.

Primary Hypothesis: Compared to healthy and hypertensive individuals, subjects with HFpEF have reduced oxidative metabolism.

Secondary Hypotheses:

- A) Oxidative metabolism is progressively impaired from healthy, to hypertensive, to HFpEF.

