20	20	20	0.012	0.010	0.009	0.01
15	15	15	0.014	0.012	0.011	0.01
25	25	25	0.010	0.009	0.008	0.01

ANOVA calculations based upon mean estimated K_{mono} in normals of 0.060 ± 0.006 .⁶

difference in K_{mono} is well within the range of difference detected between normals (0.060 ± 0.006) and patients with HFrEF (0.041 ± 0.001), previously reported by our group.^{6, 40} Of note even if sample size is reduced by 25%, we still anticipate having good power to detect a between group difference of 0.012. Therefore, using conservative sample sizes that account for potential dropout or uninterpretable images, as well as larger estimates for standard deviation than previously reported, we should have good power to detect plausible differences in oxidative metabolism between HFpEF, healthy, and hypertensive subjects.

Secondary analyses: The secondary hypotheses are presented above. In addition to testing the primary hypothesis for between group differences in K_{mono} , we will also evaluate for a significant trend across the three study groups using Spearman correlation. The relationships between oxidative metabolism and cardiac function will also be evaluated. Scatterplots and Spearman correlations will be performed with oxidative metabolism as the independent variable and measures of diastolic function as the dependent variables (mitral annular tissue Doppler e' velocities, isovolumic relaxation time, transmitral spectral Doppler E wave velocity, and E/e'). A nominal p-value threshold of < 0.05 will be used for all correlations and results meeting significance at the nominal threshold will be considered for follow up study. Similarly, we will also examine scatterplots and Spearman correlations between oxidative metabolism and systolic function (LVEF, mitral annular tissue Doppler s' velocities, and global longitudinal strain). For both systolic and diastolic parameters, we will perform multivariable linear regression analyses adjusting for age, gender, race/ethnicity, systolic blood pressure, heart rate, body mass index, LVEF, LV end diastolic volume, LV mass, and resting myocardial blood flow. We will also test for effect modification on the relationships between oxidative metabolism and diastolic and systolic function by including multiplicative interaction terms in the linear regression models. Prior to entry into regression models non-normally distributed variables will be appropriately transformed.

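### The adjusted function models in Aims 1 to 3 list LVEF as both outcome and covariate; separately, the anti-hypertensive term in the adjusted group models has no stated coding

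*Combined protocol and SAP*

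**What the plan says.** **Function models (section 3, secondary analyses).** For Aim 1 the plan examines correlations "between myocardial blood flow reserve and systolic function (LVEF, mitral annular tissue Doppler" s' velocities and global longitudinal strain). It then specifies multivariable linear regressions for systolic and diastolic measures together, "adjusting for age, gender, race/ethnicity, systolic blood pressure, heart rate, body mass index, LVEF, LV end diastolic volume, and LV mass", with no exception for LVEF. Effect modification is to be tested "by including multiplicative interaction terms in the linear regression models".

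Aim 2 repeats the pattern. The outcomes come from correlations "between oxidative metabolism and systolic function (LVEF, mitral annular tissue Doppler" s' and strain), and the covariates run to "body mass index, LVEF, LV end diastolic volume, LV mass, and resting myocardial blood flow. We will also test for effect modification". Aim 3 adopts the Aim 2 methods, with T1 "assessed in relation to features of diastolic and systolic function as previously defined above".

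**Two sources of LVEF (section 2.3).** Under Echocardiography, "LV systolic function will be assessed by LVEF, mitral annular tissue Doppler" S' and strain, which is the same set as the systolic outcomes. Cardiac MRI supplies a short-axis stack "from which LV wall thickness, mass, volumes, and ejection fraction will be determined". The plan does not say which modality supplies the covariate.

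**Group models (section 3, Analysis for aims 1 to 3).** Study group and anti-hypertensive medications enter the same model; Aim 3 takes its covariates from Aim 2. No coding is given for the drug term. Healthy subjects may take no such drug (section 2.2.1 and the detailed healthy criteria). Hypertensive subjects must take at least one (section 2.2.1 and Table 2; their detailed list only permits it). Eligibility does not fix HFpEF use.

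**The concern.** A regression of LVEF on an exposure that also conditions on LVEF cannot estimate the association it is meant to estimate. The adjusted results bearing on the secondary hypotheses about LV systolic function in Aims 1 to 3 would, for LVEF, be either an identity or an estimate pulled towards zero. A null adjusted result could then be read as evidence that the association is explained by confounding.

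The drug term raises a different question. It is zero in every healthy subject and, if coded any/none, one in every hypertensive subject. Drug effect and group difference can then be separated only through untreated HFpEF patients, if there are any. These models are the plan's stated means of dealing with confounding in the group comparison, and two of the three pairwise contrasts involve the healthy group.

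**Working it through.** The plan states no figure for these adjusted models, so there is none to reproduce.

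**1. Models affected.** Seven function measures are listed: e', isovolumic relaxation time, E velocity and E/e' (diastolic); LVEF, s' and strain (systolic). LVEF is one of the seven. With exposures MPRI, CFR, Kmono and T1, at least four adjusted LVEF models are affected.

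**2. Same measurement on both sides.** With LVEF as outcome and among the regressors, least squares fits exactly: coefficient 1 on LVEF, 0 on everything else, R-squared 1. A simulated check (n = 60, exposure, eight other covariates, LVEF and one interaction; 500 draws) gave exposure and interaction coefficients of zero to rounding error.

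**3. Echo outcome, cardiac MRI covariate.** Let each LVEF be a true value with variance 1 plus independent error with variance s² = 1/reliability − 1, and let the exposure have standardised effect β on the true value. The covariate takes coefficient (1 − β²)/(1 − β² + s²), so the share of the exposure effect remaining is

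share = s² / (s² + 1 − β²).

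Take β = 0.40, the low end of the correlations that the Aim 4 power section calls modest, so 1 − β² = 0.84. This value and the reliabilities are assumptions. Power is simulated with n = 60 and eight other covariates, 4,000 draws per row.

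| Reliability | s² | Share remaining | Power without → with LVEF covariate |
|---|---|---|---|
| 0.95 | 0.053 | 0.053/0.893 = 6% | 84% → 8% |
| 0.9 | 0.111 | 0.111/0.951 = 12% | 80% → 10% |
| 0.8 | 0.250 | 0.250/1.090 = 23% | 75% → 15% |
| 0.7 | 0.429 | 0.429/1.269 = 34% | 70% → 18% |
| 0.5 | 1.000 | 1.000/1.840 = 54% | 55% → 23% |

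For β from 0.20 to 0.50 the share is 5–7% at reliability 0.95 and 31–36% at 0.7.

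**4. Drug term, any/none coding.** Take 20 per group and k untreated HFpEF patients (k assumed), in a model with group and drug only. Without the drug term every contrast has standard error proportional to √(2/20). With it:

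- HFpEF vs healthy: √(1/k + 1/20)
- hypertensive vs healthy: √(2/20 + 1/k + 1/(20 − k))
- HFpEF vs hypertensive: √(1/(20 − k) + 1/20)

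For k = 1, HFpEF vs healthy is √(1.05/0.10) = 3.24 times larger. Ratios to the model without the drug term:

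| k | HFpEF–healthy | Hypertensive–healthy | HFpEF–hypertensive |
|---|---|---|---|
| 0 | inestimable | inestimable | 1.00 |
| 1 | 3.24 | 3.40 | 1.01 |
| 2 | 2.35 | 2.56 | 1.03 |
| 4 | 1.73 | 2.03 | 1.06 |

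Adding the nine other Aim 1 covariates, assumed unrelated to group, changes these little (HFpEF–healthy 3.27, 2.38 and 1.79 for k = 1, 2 and 4).

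**5. Drug term, count or class coding.** All contrasts are estimable. With all HFpEF patients treated and nine other covariates, assumed count distributions gave HFpEF–healthy ratios of 1.53–1.64 and HFpEF–hypertensive ratios of 1.02–1.13. Four drug classes gave 1.81–2.43 and 1.14–1.75.

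**The case against.** **On LVEF.** This is a drafting slip in one of seven function measures, in secondary analyses. The hypotheses are worded as correlations, and the Spearman correlations that address them are untouched. An R-squared of 1 would be noticed at once. All of this stands, and it limits the weight of the point. The slip would not be so visible with two modalities, where the model runs and returns a plausible but shrunken estimate.

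A reader might infer that the adjusted LVEF result is empty on either reading. The documents do not support that. They give no between-modality reliability, and the eligibility floor of LVEF at or above 50% narrows the range, which tends to lower reliability. About a third of the effect remains at 0.7 and over half at 0.5. The value 0.40 is also borrowed from a different set of associations.

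**On the drug term.** A reader might infer that the adjusted group models are bound to be rank-deficient. That needs any/none coding and no untreated HFpEF patient, and the plan states neither. Nor do the adjusted models fall short of promised power: the power statements for Aims 1 to 3 concern the one-way ANOVA, and none is made for the adjusted models. Omitting the drug term is also partly a trade-off, since it exchanges imprecision for a contrast that contains any drug effect.

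Finally, a reader might suppose that the three-group model makes a separate HFpEF-versus-hypertensive model redundant. The two estimates coincide only when the model has group and drug alone. With nine further covariates, count coding and SD 0.90, simulated estimates differed with an SD of 0.11 CFR units.

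**Conclusion.** The LVEF point holds on the text and is small in scope. The adjusted LVEF models in Aims 1 and 2, and in Aim 3 by reference, are wrong as written. With one measurement the result is an identity, and this needs no assumption. With two modalities the effect is strongly shrunk, by an amount that depends on the assumed reliability and effect size. The Spearman correlations, the other six function measures and the primary group tests are unaffected.

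The drug-term point is a secondary, conditional note. What the documents establish is that coding is unstated while use is fixed at none in the healthy group and at one or more in the hypertensive group. The loss of the healthy contrasts, or a three-fold larger standard error, follows only under any/none coding with no or very few untreated HFpEF patients. Under count or class coding the loss of precision is moderate. The HFpEF-versus-hypertensive contrast is little affected under any/none or count coding, and more so with several classes.

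**What to change.** 1. When LVEF is the dependent variable, remove LVEF of either modality from the covariates, in both the main-effect and the interaction models for Aims 1 to 3. Keep it as a covariate for the other function measures and state which modality supplies it.
2. In the adjusted group models, avoid any/none coding of anti-hypertensive medications and fix the coding (count or class) before analysis. Count cost less precision than four classes under the distributions tried here.
3. Report the adjusted contrasts with healthy subjects also from a model without the drug term, and say that these include any drug effect.

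The cost is a few sentences of SAP wording, with no new data or subjects. The price of item 3 is a second set of adjusted contrasts that must carry its caveat.
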